2.2 Analysis sets

The following analysis populations will be defined for statistical analysis:

- **Screened (SCR) set** – All patients who have signed informed consent. The screened set includes only unique screened patients, i.e., in the case of re-screened patients only the chronologically last screening data is counted.
- **Randomized (RAN) set** – All patients who received a randomization number, regardless of receiving trial medication.
- **Safety set (SAF)** - All randomized patients who received at least one dose of study drug. Patients in the SAF will be analyzed according to treatment received.
- **Full analysis set (FAS)** – All patients in the RAN population who were not mis-randomized patients*. Following the intent-to-treat (ITT) principle, patients in the FAS are analyzed according to the treatment they have been assigned to at the randomization.
- **Per-protocol set (PPS)** will be a subset of the FAS which will consist of the patients who do not have major deviations. Major protocol deviations will be pre-specified prior to unblinding.

* Mis-randomized patients are those who were not qualified for randomization and who did not take study drug, but have been inadvertently randomized into the study.

Subjects without valid written informed consent will be excluded from all analysis sets.

A sample of rules leading to exclusion from specific analysis sets of patients violating protocol specified inclusion/ exclusion criteria and any other protocol deviations developed during the study has been provided in [Appendix 5](#). The final list may be different from this which will be finalized and signed off before DBL.

2.2.1 Subgroups of interest

Subgroups will be formed to explore the consistency of treatment effects and safety profiling on selected parameters between the subgroups and the overall population. In general, subgroups will be defined based on baseline information as defined in [section 2.1](#).

In Table 2-1, we have listed all subgroups defined for this study and the ways to derive them. Subsets of these subgroups will be used depending on the parameter under consideration. Also note that only important parameters or variables in these analyses will have subgroup analyses. The details about the parameters having subgroup analyses will be presented in the corresponding sections as appropriate. Also, additional subgroups may be formed later for regional or country-wise analyses as applicable.

Table 2-1 Specification of subgroups

Subgroup	Method of derivation	Disposition/ Background & Demographics / Exposure	Efficacy	Safety
Number of cardiovascular (CV) risk factors (1 CV risk factor vs. > 1 CV risk factor) ¹	Screening		X	
Age groups: (<65 vs. ≥65 years, <75 vs. ≥75 years)	Screening (derived)	X	X	X
Gender (male/ female)	Screening	X	X	X
Race	Screening	X	X	X
Region*	Derived (pooled countries or country), using Screening	X	X	X
Baseline LVEF (by quartiles)	Screening		X	
Baseline LVEF ≤40% vs. > 40%	Screening		X	
Worst Killip class (I vs. ≥ II)	Randomization		X	
Type of MI (STEMI vs. NSTEMI)		X	X	X
Infarct location (anterior, inferior, and other)			X	
PCI use at baseline (PCI use versus medical management after index MI)	Randomization	X	X	

Subgroup	Method of derivation	Disposition/ Background & Demographics / Exposure	Efficacy	Safety
Time from the index MI presentation to randomization (< median, ≥median)			X	
Baseline SBP (three groups: ≤110 mmHg; >110 mmHg and ≤140 mmHg; >140 mmHg)	Randomization		X	
Screening eGFR (<60 vs ≥ 60 mL/min/1.73 m ²)			X	
History of diabetes (yes/no)	Screening		X	
Atrial Fibrillation associated with index MI at baseline (yes/no)			X	
Prior history of MI			X	
History of hypertension (yes/no)	Screening		X	
Prior ACEi or ARB use (yes/no)			X	
Use of β-blocker at baseline (yes/no)			X	
Use of mineralocorticoid antagonists at baseline (yes/no)	Randomization		X	
Use of loop diuretics at baseline (yes/no)			X	

* **North America:** Canada, USA

¹ Patients with no CV risk factor are categorized in the "1 CV risk factor" group.

Latin America (including Central America): Argentina, Peru, Brazil, Colombia, Mexico

Western Europe: Austria, Belgium, Denmark, Finland, France, Germany, Italy, Netherlands, Norway, Portugal, Spain, Sweden, Switzerland, United Kingdom

Central Europe: Bulgaria, Croatia, Czech Republic, Greece, Hungary, Poland, Romania, Russia, Slovakia, Turkey

Asia Pacific & Others: Australia, South Africa, Israel, China, India, Korea, Philippines, Singapore, Taiwan, Thailand

2.3 Patient disposition, demographics and other baseline characteristics

2.3.1 Patient disposition

Based on all patients in the screened set, number and percentage of patients screened successfully will be provided. In addition, screen failure patients will be summarized by primary reason for screen failure.

The number and percentage of randomized patients included in different analysis sets (Section 2.2) will be summarized based on the randomized patients. Patients with premature study discontinuation during the double-blind treatment epoch will be summarized by the primary reason of discontinuation for each randomized treatment group and overall based on all patients in randomized set (RAN).

In addition, the number and percentage of patients with protocol deviations as well as the criteria leading to exclusion from analysis sets will be provided for the patients in randomized set (RAN). All the disposition data will also be listed at a patient level for double-blind period disposition.

The number and percentage of patients with any and each of the following COVID-19 impacted criteria will be provided for all randomized patients, patients randomized prior to 1-Mar-2020, and patients randomized on or after 1-Mar-2020: (1) cancelled/rescheduled doctor's appointment due to COVID-19; (2) cancelled/rescheduled procedure due to COVID-19; (3) missed study visit due to COVID-19; (4) study visit performed outside the study site due to COVID-19; (5) study assessment or visit procedures changed due to COVID-19; (6) method of dispensing the study drug to the subject changed due to COVID-19; (7) study drug interruption due to COVID-19; (8) study drug discontinuation due to COVID-19; (9) endpoint(s) impacted by COVID-19; (10) had symptom(s) for which the patient felt the need to go to an outpatient clinic, urgent care, emergency department, or hospital but chose not to due to COVID-19.

2.3.2 Demographics and baseline characteristics

Following demographic and baseline characteristics will be summarized by randomized treatment group for all patients in full analysis set (FAS):

- **Continuous variables**

Age (in years), height (in centimeters), weight (in Kg.), body mass index (BMI) in Kg/m², SBP (in mmHg), DBP (in mmHg), heart rate (in bpm), eGFR (in ml/min/1.73m²),

- **Categorical variables**

- Age group (<65 years vs. ≥65 years; <75 years vs. ≥75 years)
- Sex
- Race
- Ethnicity
- Region

2.3.2.1 Characteristics and therapies associated with qualifying MI

Qualifying MI related characteristics, cardiovascular (CV) risk factors associated with qualifying MI and therapies used to manage qualifying MI will be summarized separately for all patients in the Full Analysis set (FAS) which includes:

- **Disease characteristics**

Time from index MI presentation to randomization,

Location of infraction (anterior / inferior), type of MI (STEMI/ NSTEMI), number of diseased vessels, ejection fraction (EF) (in %), Killip class

- **CV risk factors/co-morbidity/past history at baseline**

Age (<70, ≥70 years), screening eGFR (<60, ≥60 ml/min/1.73m²), diabetes (yes/no), history of prior MI (yes/ no), atrial fibrillation associated with qualifying MI (yes/ no), categories of EF (<30%, ≥30%), worst Killip class (<III, ≥III), STEMI without reperfusion therapy within the first 24 hours after presentation (yes/no).

Number of CV risk factors will be summarized descriptively.

- **Therapies used to manage qualifying MI –**

Use of reperfusion therapies (yes / no) –

- use of PCI (yes/ no) (including procedures performed for qualifying MI both prior to and after randomization but before discharge)
- type of stenting if PCI performed (bare metal/drug eluting stent)
- use of antithrombotic therapy (yes/no) which includes aspirin, P2Y12 inhibitor, antithrombin agents, glycoprotein (GP) IIb/IIIa inhibitors
- use of oral CV medications including (but not limited to) ARB/ACE inhibitors, beta blockers, mineralocorticoid receptor antagonists (MRA), statins, oral anticoagulants, non-loop diuretics, loop diuretics, digitalis glycosides, oral nitrates and calcium channel blockers..
- use of IV diuretics (yes/no), IV vasodilator (yes/no), IV vasopressors (yes/no), IV inotropes (yes/no)

In general, all continuous variables will be summarized by presenting descriptive statistics (n, mean, SD, Q1, Q3, median, minimum, maximum) and all categorical variables will be summarized by number and percentage of patients in each category. The summaries will be provided by randomized treatment group for all patients in Full Analysis set (FAS).

2.3.3 Medical history

Any condition entered on the relevant medical history / current medical conditions CRF will be coded using the most updated version of MedDRA dictionary. Medical history includes cardiovascular disease history and other medical history in this study, which are collected at Visit 1 (Screening visit). The number and percentage of subjects with each medical condition will be provided by treatment group and system of organ class and preferred term for the Full Analysis Set (FAS).

Patient disposition, demographic/ baseline and other disease characteristics will also be summarized similarly for the following subgroups:

- Age group (<65 vs. ≥65 years), age group (<75 vs. ≥75 years)

- Gender (male/female)
- Region
- Race
- Type of MI (STEMI vs. NSTEMI)
- PCI use at baseline (Yes vs. No)

2.4 Treatments (study treatment, rescue medication, concomitant therapies, compliance)

2.4.1 Study treatment / compliance

Overall treatment exposure

The duration of overall treatment exposure (in days) will be calculated as –

Last known date when the patient took study medication – Date of 1st intake of randomized study medication during double-blind treatment epoch + 1

This includes days patient is off-treatment due to temporary treatment interruption.

The overall treatment exposure duration (in days) will be summarized by randomized treatment group using mean, standard deviation, median, minimum and maximum. Additionally, the treatment exposure duration will also be summarized categorically by presenting number and percentage of patients with exposure

- <2 weeks
- 2 to < 4weeks
- 4weeks to < 6months
- 6months to < 1 year
- 1 year to < 2 years
- >= 2 years

Mean daily dose and mean dose level for each patient will be summarized by treatment group. Mean daily dose and mean daily dose level for each patient will be calculated as –

$$\frac{\sum_{i=0}^3 (\text{Number of days spent on Dose}_i) X (\text{Dose}_i)}{\sum_{i=0}^3 (\text{Number of days spent on Dose}_i)}$$

For mean daily dose calculation ‘Dose_i’ represents actual dose (in mg) administered at dose level ‘i’ according to [Table 1-1](#), whereas for mean daily dose calculation ‘Dose_i’ represents the categorical dose level (0, 1, 2 or 3) administered at dose level ‘i’. Further, dose level ‘0’ refers to zero dose signifying treatment interruption. Mean daily dose and mean daily dose level calculated as above will be summarized by treatment groups for overall study duration. Mean doses and mean dose levels of study drug at each visit will also be summarized by treatment group and visit. Last dose and last dose level when patients are alive will also be summarized by treatment group.

Descriptive summary of number of days spent at each dose level as mentioned in [Table 1-1](#) will be provided by treatment group. Also, number and percentage of randomized patients at each

dose level will be summarized by visit and treatment group. Time to first reach the dose at each dose level and time to first reach the target dose will be summarized for each treatment group during the double-blind treatment epoch. In addition, reasons for down-titrating treatment will be summarized by each treatment group for each dose level.

Time to permanent discontinuation of study medication not due to death will be summarized according to the Kaplan-Meier analysis. A summary table by treatment group will be provided to display the number and percentage of patients who discontinued study medication by the primary reason for discontinuing and the number and percentage of patients who subsequently received the following medications during the study: ACE inhibitors, ARB, and Entresto™ (sacubitril/valsartan). Exposure durations will be summarized by treatment group for these medications. The last doses and dose levels of study drugs for these switchers will also be summarized by treatment group.

Overall study drug exposure

Duration of overall study drug exposure is defined as the duration of treatment exposure (in days) excluding days of treatment interruption and is calculated as –

(Last known date when the patient took study medication – Date of 1st intake of randomized study medication during double-blind treatment epoch + 1) – number of days of treatment interruption

The duration of study drug exposure (in days) will be summarized by randomized treatment group using mean, standard deviation, median, minimum and maximum. Additionally, the treatment exposure duration will also be summarized categorically by presenting number and percentage of patients with exposure

- <2 weeks
- 2weeks to < 4weeks
- 4weeks to < 6months
- 6months to < 1 year
- 1 year to < 2 year
- \geq 2 years

Treatment and study drug exposure in subgroups

Both overall treatment exposure and overall study drug exposure will be summarized by the following subgroups -

- Age group (< 65 vs \geq 65 years; < 75 vs \geq 75 years)
- Gender
- Race
- Region
- Type of MI (STEMI vs. NSTEMI)

Overall study exposure (Follow-up duration)

Following the definition of double blind phase in section 2.1.1, for each patient duration of study exposure (in days) during double blind phase is calculated as total duration of on-treatment randomized phase and post-randomized treatment phase where –

Duration of on-randomized treatment phase (in days) is calculated as –

Date of last study drug intake – randomization date + 1.

Duration of post-randomized treatment phase or off-treatment phase (in days) is calculated as –

min(Last date patient is known to be alive, Last visit date before analysis cutoff date) –
Last known date patient took randomized study medication + 1

Hence, overall study exposure duration (follow-up duration) = Duration of on-randomized treatment phase + Duration of post-randomized treatment phase – 1.

Of note, for randomized patients not receiving double-blind randomized study medication, overall study exposure duration is calculated as –

min(Last date patient is known to be alive, Last visit date before analysis cutoff date) –
randomization date + 1

The duration of overall study exposure and on-treatment randomized phase are summarized by randomized treatment group for all patients in FAS by providing descriptive statistics (n, mean, SD, Q1, Q3, median, minimum, maximum).

2.4.2 Prior, concomitant therapies

‘**Prior medications**’ are defined as drugs taken prior to first dose of double-blind study medication. Any medication which has been started during the double-blind treatment epoch including medications started prior to randomization but continued in the double-blind treatment epoch are identified as ‘**Concomitant medications**’.

Prior and Concomitant medications will be summarized separately by therapeutic class (by ATC code), preferred term, and treatment group for the safety set. Prior and Concomitant non-drug therapies will be summarized separately by SOC, preferred term, and treatment group for the safety set. The number and percentage of patients on following CV background medications during double-blind treatment epoch will be tabulated by randomized treatment group –

- Aspirin
- Antiplatelet agents (excl. Aspirin)
 - P2Y12 inhibitors
 - Glycoprotein (GP) IIb/IIIa inhibitors
 - Other

- ARBs
- ACE inhibitors
- Beta Blockers

- Mineralocorticoid Receptor Antagonists
- Statins
- Diuretics (Loop/non-loop diuretics, summarized by IV/ oral diuretics)
- Cardiac glycosides (Digoxin/digitalis glycoside)
- Calcium channel blockers
- Anticoagulants
- Antiarrhythmic agents
- Nitrates
- Other lipid lowering agents
- Anti-diabetic drugs
 - Insulins
 - Oral anti-diabetic drugs
- Other

Apart from the CV medications listed above, reperfusion therapies used during post-randomized treatment phase for managing index MI and any other post-randomization MI will be summarized separately in a similar way as in [section 2.3.2.1](#). The summaries of background medications and non-drug therapies will be provided for Safety set (SAF) unless otherwise specified.

Analysis of dose intensity of RAS blockade during double-blind period

Dose intensity of RAS blockades during double-blind period will be captured in terms of mean total daily dose levels of open label ARB/ACEIs/Entresto used after study drug discontinuation. Mean total daily dose for each study medication is defined by average of different doses for the medications (including no or zero dose) weighted by number of days patient is on that dose during the specified analysis period. The total daily dose of RAS blockades (high/low) are categorized based on the [table 2-2](#) below.

Table 2-2 Definition of high and low RAAS blockade group based on total daily dose of commonly used ARB/ACEIs

ARBs	Low RAAS blockade group	High RAAS blockade group	ACEIs	Low RAAS blockade group	High RAAS blockade group
Azilsartan	<80 mg	≥ 80 mg	Enalapril	<10 mg	≥ 10 mg
Candesartan	<16 mg	≥ 16 mg	Benazepril	<20 mg	≥ 20 mg
Eprosartan	<400 mg	≥ 400 mg	Captopril	<100 mg	≥ 100 mg
Irbesartan	<150 mg	≥ 150 mg	Cilazapril	<2.5 mg	≥ 2.5 mg
Losartan	<50 mg	≥ 50 mg	Delapril	<30 mg	≥ 30 mg
Olmesartan	<10 mg	≥ 10 mg	Fosinopril	<20 mg	≥ 20 mg
Telmisartan	<40 mg	≥ 40 mg	Imidapril	<10 mg	≥ 10 mg
Valsartan	<160 mg	≥ 160 mg	Lisinopril	<10 mg	≥ 10 mg
			Moexipril	<7.5 mg	≥ 7.5 mg
			Perindopril	<4 mg	≥ 4 mg
			Quinapril	<20 mg	≥ 20 mg

ARBs	Low RAAS blockade group	High RAAS blockade group	ACEIs	Low RAAS blockade group	High RAAS blockade group
			Ramipril	<5 mg	≥ 5 mg
			Spirapril	<6 mg	≥ 6 mg
			Temocapril	<2 mg	≥ 2 mg
			Trandolapril	<2 mg	≥ 2 mg
			Zofenopril	<30 mg	≥ 30 mg

For patients taking open-label Entresto, total mean daily dose is categorized into high/low dose level according to LCZ696 dose levels 50mg bid (low), 100 mg bid (high), 200 mg bid (high). The open label ARB/ACEI and open-label Entresto/LCZ696 dose level will be considered to determine whether a patient is on high or low dose level of RAS blockade.

Overall mean total daily dose levels of open label ARB/ACEIs/Entresto will be summarized for the double-blind period for each treatment group by providing number and percentage of patients on high and low dose level during the first 12 months from randomization for the following patient populations -

- FAS
- FAS patients who discontinue study treatment during the first 12 months after randomization.

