Figure 3-2 Study drug initiation and up-titration in PARADISE-MI

* [ACEi/ARB: Yes] is defined as receiving ACEi or ARB during the last 24 hours prior to randomization

† At Investigator's discretion and patient clinical condition, dose level 2 can be initiated for [ACEi/ARB: Yes] patients

Patients randomized to LCZ696, who receive their last dose of ACEi within 36 hours prior to randomization, will receive two doses of blinded valsartan at 40 mg (level V1) or 80 mg (level V2) according to Investigator's discretion

The starting dose level of the study drugs will be determined based on the patient's clinical condition and taking into consideration their prior standard background therapy. Patients who did not receive an ACE inhibitor or ARB in the last 24 hours prior to randomization (ACE inhibitor/ARB No patients) will start at dose level 1. Patients who did receive an ACE inhibitor or ARB in the last 24 hours prior to randomization (ACE inhibitor/ARB Yes patients) will start at dose level 1, or at investigator's discretion, dose level 2, after taking into consideration the patients' prior dose level of ACE inhibitor/ARB therapy (Table 3-2) and clinical condition (SBP, renal function, etc.).

Table 3-2 Total daily doses of commonly used ACE inhibitors and ARBs corresponding to dose level 2 of study drug

ACE inhibitor	Dose	ARB	Dose
Benazepril	20 mg	Azilsartan	40 mg
Captopril	100 mg	Candesartan	16 mg
Cilazapril	2.5 mg	Eprosartan	400 mg
Enalapril	10 mg	Irbesartan	150 mg
Fosinopril	20 mg	Losartan	50 mg
Imidapril	10 mg	Olmesartan	10 mg
Lisinopril	10 mg	Telmisartan	40 mg
Moxepril	7.5 mg	Valsartan	160 mg
Perindopril	4 mg		
Quinapril	20 mg		
Ramipril	5 mg		
Trandolapril	2 mg		
Zofenopril	30 mg		

ACE inhibitor/ARB No patients (no treatment with ACE inhibitor/ARB therapy during the 24 hours prior to randomization):

- Start at dose level 1, if SBP is ≥ 110 mmHg

ACE inhibitor/ARB Yes patients (treated with ACE inhibitor/ARB therapy during the 24 hours prior to randomization):

- Start at dose level 1, if SBP is ≥ 100 mmHg OR
- At investigator's discretion, patients may also start at dose level 2, taking into consideration patient's prior dose level of ACE inhibitor/ARB therapy (Table 3-2) and clinical condition (SBP, renal function, etc.).

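### Azilsartan's cut-off for high RAAS blockade in SAP Table 2-2 (80 mg/day) is twice the protocol's dose-level-2 equivalent (40 mg/day), while the other 20 drugs in both tables match

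*SAP*

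**What the plan says.** Protocol section 3.1, Table 3-2, is titled "Total daily doses of commonly used ACE inhibitors and ARBs corresponding to dose level 2 of study drug". Its first row is "Benazepril 20 mg Azilsartan 40 mg". The table helps the investigator choose a starting level from the patient's previous ACE inhibitor or ARB dose.

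SAP section 2.4.2, Table 2-2, is titled "Definition of high and low RAAS blockade group based on total daily dose of commonly used ARB/ACEIs". Its azilsartan row is "Azilsartan <80 mg ≥ 80 mg". Other ARB rows include "Candesartan <16 mg ≥ 16 mg" and "Valsartan <160 mg ≥ 160 mg". For open-label Entresto, the text below the table gives the rule "LCZ696 dose levels 50mg bid (low), 100 mg bid (high), 200 mg bid (high").

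In the current SAP the classification covers open-label ARBs, ACE inhibitors and Entresto taken after study drug is stopped. It uses each patient's mean total daily dose, weighted by days at each dose, with zero-dose days counted. Numbers and percentages in the high and low groups are reported by treatment arm for the first 12 months after randomisation. They are given for the FAS and for FAS patients who discontinued study treatment in that period.

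Both azilsartan entries are unchanged across versions: 40 mg in the original and the amended protocol, 80 mg in the original and the amended SAP.

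**The concern.** A high/low split pooled over many drugs can be interpreted only if each drug is cut at a comparable dose. The two tables use the same unit, total daily dose, and nearly the same drug list, and they agree everywhere that can be checked except for azilsartan. If dose level 2 is the intended boundary, azilsartan users must reach twice that level to be counted as high, and users of the other shared drugs need only reach it.

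What is at stake is the accuracy of the high and low counts in this summary. Any azilsartan user whose mean falls between the two figures is placed on a different scale from the rest of the table. No efficacy estimate is involved.

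**Working it through.** **Inputs.** Protocol Table 3-2 lists 21 drugs (8 ARBs, 13 ACE inhibitors). SAP Table 2-2 lists 24 (8 ARBs, 16 ACE inhibitors). The protocol's Moxepril is taken as the SAP's Moexipril.

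**Overlap.** Three ACE inhibitors (delapril, spirapril, temocapril) are in the SAP table only, so 24 − 3 = 21 drugs are shared.

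**Rule tested.** SAP cut-off for high = protocol total daily dose for dose level 2.

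**Result, drug by drug (mg/day, same figure in both tables):**

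- ARBs: candesartan 16, eprosartan 400, irbesartan 150, losartan 50, olmesartan 10, telmisartan 40, valsartan 160. Seven of 8 match.
- ACE inhibitors: benazepril 20, captopril 100, cilazapril 2.5, enalapril 10, fosinopril 20, imidapril 10, lisinopril 10, moexipril 7.5, perindopril 4, quinapril 20, ramipril 5, trandolapril 2, zofenopril 30. Thirteen of 13 match.
- Azilsartan: SAP 80, protocol 40. Ratio 80 / 40 = 2.0.

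In total 7 + 13 = 20 of 21 match, with one exception.

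**Cross-check against the study-drug dose levels (protocol Table 3-1).** Ramipril level 2 is 2.5 mg twice daily, 2 × 2.5 = 5 mg/day, which equals the SAP ramipril cut-off. LCZ696 level 2 is 100 mg twice daily, which the SAP counts as high when taken as open-label Entresto. Both fit a boundary at dose level 2.

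**Who is affected.** On the protocol's scale, a mean azilsartan dose of 40 to below 80 mg/day is 1 to below 2 times the level-2 dose. The same multiple is 16 to below 32 mg for candesartan and 160 to below 320 mg for valsartan. The SAP counts both of those ranges as high and the azilsartan range as low.

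The mean includes zero-dose days, so the affected group is defined by the mean and not by the prescribed dose. Let f be the fraction of counted days on drug:

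- Constant 40 mg gives a mean of 40f. With any zero-dose day (f < 1) this is below 40 and low under either figure. Only f = 1 gives a mean of 40, where the two figures disagree.
- Constant 80 mg gives a mean of 80f. It reaches 80 only if f = 1, and reaches 40 if f is at least 0.5. The two figures therefore disagree for f from 0.5 to below 1.

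The documents do not say how many patients took open-label azilsartan, so the change in counts cannot be computed.

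**The case against.** The strongest reply is that the SAP never says Table 2-2 is taken from protocol Table 3-2, or that its cut-offs are level-2 equivalents. The tables serve different purposes: one guides the choice of starting level, the other classifies open-label treatment after discontinuation. This stands as a limit. The common basis is inferred from 20 exact matches in 21 and from the Entresto and ramipril figures. It is a strong inference, but the accurate description is an unexplained inconsistency, and a deliberate separate basis for azilsartan cannot be excluded.

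A second reply is that the consequence is minor. This stands in full. The output is a count and percentage in one descriptive table.

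Three stronger readings are tempting, and the documents do not support them:

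- A reader might infer that azilsartan differs from every other drug in the SAP table. Delapril, spirapril and temocapril have no protocol counterpart, so the comparison covers only the 20 other shared drugs and open-label Entresto.
- A reader might infer that azilsartan is being compared with blinded study drug at level 2. The original SAP combined blinded and open-label doses in this summary. The current SAP classifies only open-label agents, so the comparison runs through open-label Entresto.
- A reader might infer that the table decides whether blockade after discontinuation was adequate, or whether the treatment effect was diluted. The SAP presents it as dose intensity and assigns it no such role. Switching to open-label Entresto is handled by the IPCW analyses of secondary endpoints (1), (3) and (5) and by a redefined count for endpoint (4) (SAP 2.6.5). None of these uses Table 2-2.

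**Conclusion.** The inconsistency is real. The azilsartan figures differ by a factor of 2, the difference is present in both versions of each document, and no footnote or text explains it. As the plan stands, a mean open-label azilsartan dose of 40 mg to below 80 mg per day is counted as low, although the equivalent mean dose of any other shared drug is counted as high.

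This is a minor, housekeeping-level correction. It can change the high and low counts in one descriptive summary, by an unknown and possibly small number of patients. The conclusion assumes that one equivalence basis was meant for all agents, which the SAP does not state. If the protocol entry is the one that needs changing, the SAP counts would stay as they are and the correction would fall on the starting-dose table.

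**What to change.** Reconcile the azilsartan entries in SAP Table 2-2 and protocol Table 3-2 so that the high/low classification uses one equivalence basis for all agents. Alternatively, add a footnote to Table 2-2 stating why azilsartan's basis differs. It would also help to state in SAP 2.4.2 what the cut-offs represent and where those for the three SAP-only ACE inhibitors come from. The sponsor must determine which azilsartan figure is right; no dose is proposed here.

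If the SAP row changes, the cost is one table row and the matching line of programming before database lock. If the protocol entry changes, it is a correction to starting-dose guidance and goes through the protocol's amendment process. A footnote costs one sentence.
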